**“Metabolism of 0.35mg Norethindrone vs 5mg
Norethindrone Acetate”**

NCT05294341

7/09/2024

Background:

Norethindrone has an elimination half-life of about 8 hours. Norethindrone acetate has an initial disappearance with half life of 7.5 minutes, with subsequent elimination half-life of 51.5 hours. Singh et. al. demonstrated that equilibrium was reached between NET and NETA 24-48 hours. Prior to 24 hours, norethindrone predominates. After 72 hours, norethindrone acetate predominates. This study suggested that the prolonged half life of norethindrone acetate contributes to prolonged action of norethindrone acetate

Study Objectives:

Specific Aim 1: To assess the relative bioavailability of norethindrone in individuals taking 5mg norethindrone acetate vs 0.35mg norethindrone

Specific Aim 2: To assess the maximum and minimum norethindrone concentrations in individuals taking 5mg norethindrone acetate vs 0.35mg norethindrone

Specific Aim 3: To assess the differences in serum levels of estradiol, LH, FSH, and progesterone levels in individuals taking 0.35mg norethindrone vs 5mg norethindrone acetate

Hypothesis: The relative bioavailability of norethindrone will be comparable in individuals taking 5mg norethindrone acetate vs 0.35mg norethindrone.

Design:

We will collect patient serum samples over the course of a week to assess for amount of norethindrone in their blood. We will also examine estradiol, follicle stimulating hormone, luteinizing hormone, and progesterone levels at various timepoints in the study. We will have patients fill out a symptom diary to document bleeding profile and side effects from their medications. This symptom diary will also have patients demonstrate satisfaction on their therapy.

Subjects in each group will be assigned either 0.35mg norethindrone or 5 mg norethindrone acetate as their initial therapy. They will start taking either medication on day 1 of their menstrual cycle. Serum levels will be drawn at 8 am for 7 days. On day 8 they will stop taking norethindrone, and will have their serum levels drawn hourly for 8 hours. They will then undergo a 1 month washout. They will do the above with the opposite therapy.

The blood draws will take place in the Clinical Research Center on the 4th floor. The samples will be stored in the Clinical Research Center freezers. [name] will then analyze the amount of norethindrone there is in each assay.

Methods:

This study was conducted at the Milton S. Hershey Medical Center College of Medicine, and Penn State Health's Outpatient Obstetrics and Gynecology clinic. Institutional Review Board (IRB) approval was obtained through the Penn State College of Medicine IRB. Study participants provided written informed consent as part of their enrollment into the study.

Study Participants

Women aged 18-55 years old, with menstrual length cycles 24-34 days, , using reliable non-hormonal contraception (permanent contraception or copper IUD), and the ability to follow-up, were eligible for the study. Participants were excluded if they were pregnant within the last 3 months had a history of irregular menstrual cycles, on hormonal contraception, hormone replacement therapy, or hormonal treatment of infertility in the last 3 months, history of

hysterectomy, liver disease, kidney disease, breast cancer, venous thromboembolism. . Potential subjects were identified directly in the clinical setting during clinic visits by the PI and co-I or identified by medical records review of individuals who had undergone bilateral tubal sterilization procedures for undesired fertility in the last 6 months. They were called by the co-I to assess interest in the study, and times were arranged to consent the subject in person.

Study Treatment

NETA and NET tablets were packaged and supplied by the Investigational Drug Service (IDS) Pharmacy. Paper scripts for each treatment were provided to the subjects, and were filled and distributed by the IDS.

Study Design

This is a cross-sectional pilot study examining serial plasma concentrations of norethindrone, luteinizing hormone, follicle stimulating hormone, estradiol, and progesterone in individuals taking either NET or NETA.

There was no randomization process. The study was divided into 2 arms with the same protocol and procedures for each arm. The first half of subjects recruited were assigned to NET as their initial intervention. The second half of subjects were assigned to NETA as their initial intervention. Neither subjects nor study coordinators were blinded to medication assignment. However, the laboratory personnel were blinded to the medications assigned in each sample analyzed.

Subjects were instructed to begin taking their assigned medication on days 1-3 of their menstrual cycle. They received text message reminders to take their medication between 6:30-8:00AM daily. Within one hour of self-administering the medication, they presented to Penn State Health Milton S. Hershey Medical Center, for phlebotomy to measure concentrations of plasma norethindrone. This was repeated for 7 days. On day 8 subjects stopped taking their medication, and initiated pharmacokinetic (PK) testing with hourly blood draws for 8 hours to assess their norethindrone levels. They then underwent a 1-month washout, after which the above was repeated with the opposite medication. Additionally, we drew phlebotomy for estradiol, follicle stimulating hormone, luteinizing hormone, and progesterone levels at days 1, 8, and 21 of each phase. Blood samples were centrifuged immediately after collection, and plasma was collected and stored in a -40C freezer until ready for analysis.

Days 1-8 of both phases, subjects completed a symptom diary to document bleeding profile and side effects. The symptom diary included: irregular bleeding, changes in menstrual cycle, changes in vaginal discharge, nausea, vomiting, headaches, weight gain, mood changes, breast pain, abdominal pain, abdominal bloating, pelvic pain, swelling of the legs, and other. A validated bleeding quantification tool was also included. . At the end of day 8, subjects completed a survey that assessed the following: subject satisfaction with their medication, whether they experienced any side effects, whether they experienced any improvement in preexisting symptoms, and whether the subjects had additional feedback. The Symptom Diary was filled out on days 1-8 for each phase, and returned to the site at the Day 8 PK visit of phase 2. At the end of the study, each participant completed an additional survey about the feasibility of study, including taking their medication at the same time every day, presenting for daily blood draws at the same time every day, and obtaining hourly blood draws on day 8.

Study Endpoints and Measurements

Analysis of norethindrone in plasma

Chemicals

Norethindrone was purchased from Sigma-Aldrich (St. Louis, MO) and ¹³C₂-norethindrone was purchased from Cambridge Isotope Laboratories (Tewksbury, MA).

Analysis of plasma drug levels

Plasma concentrations of norethindrone were determined using mass spectrometry. Standard curves were constructed by plotting the ratio of the analyte peak area to internal standard peak area versus analyte concentration. The standard working solution (4 mL) and internal standard (4 mL) were spiked into control plasma (10 mL), and after vortexing, acetonitrile/H₂O/formic acid (90/10/0.1) (22 mL) was added to extract the analytes from plasma. Proteins were precipitated by vortexing with subsequent centrifugation at 8,765 g for 10 minutes at 4°C. The supernatant was taken and loaded to the HPLC/MS/MS system, with final concentrations of 1 ng/mL to 1000 ng/mL for norethindrone.

For norethindrone analysis, after spiking 4 mL ¹³C₂-norethindrone into 200 mL plasma, 600 mL acetonitrile/H₂O/formic

acid (90/10/0.1) was added for extraction. The supernatant was dried and the residue was reconstituted by 40 mL acetonitrile/H₂O/formic acid (90/10/0.1) before loading onto HPLC-MS-MS system. The calculated concentrations from the standard curves were divided by 5 to reflect the in vivo levels of norethindrone in plasma.

Norethindrone in plasma was analyzed using a Sciex QTRAP 6500+ mass spectrometry coupled with a Sciex EXion HPLC separation system. A 1.7 mm Acquity UPLC BEH C18 analytical column (2.1 x 100 mm, Waters, Ireland) was used. The gradient elution was conducted using a flow rate of 0.4 mL/min with the following conditions: initial at 70% mobile phase B (acetonitrile) and 30% mobile phase A (0.1% formic acid in water), followed by a linear gradient to 90% mobile phase B in 1 minute, and kept at 90% mobile phase B for 3 additional minutes to flush the column before bringing back to initial conditions to equilibrate the column.

The Sciex QTrap 6500+ mass spectrometer was equipped with an electrospray ionization probe operated in positive mode. The decluster potential (DP) was 131 V; the entrance potential (EP) was 10 V, the collision energy (CE) was 25 V, while the collision cell exit potential (CXP) was 12 V. The curtain gas (CUR) was 35 L/h, the collision gas (CAD) was medium. The ionSpray voltage was 5500 V, the temperature was 600 °C, gas 1 was 15 L/h, and gas 2 was 15 L/h.

The multiple reaction monitoring mode (MRM) was used to analyze and quantify norethindrone and ¹³C₂-norethindrone, with the transitions of 299 > 231 for norethindrone, 301 > 231 for ¹³C₂-norethindrone. All peaks were integrated and quantified by Sciex OS 1.5 software.

Statistical Analysis Plan

Serum Levels of norethindrone were averaged across all subjects on days 1 through 7. This was done for individuals taking both 5mg norethindrone acetate and 0.35mg norethindrone. Standard deviations for each of these averages were calculated. Serum levels of norethindrone were then averaged across all subjects on hours 0-8 on day 8 of the study. This was done for individuals taking both 5mg norethidnrone acetate and 0.35mg norethindrone. Standard deviations for each of these averages were calculated.

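### Aim 1 promises relative bioavailability, but the plan as written estimates the relative norethindrone exposure of two regimens whose norethindrone content differs about 12.5-fold

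*Combined protocol and SAP*

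**What the plan says.** Under Study Objectives, Aim 1 is "To assess the relative bioavailability of norethindrone in individuals taking 5mg norethindrone acetate vs 0.35mg norethindrone". The hypothesis is "The relative bioavailability of norethindrone will be comparable in individuals taking 5mg norethindrone acetate vs 0.35mg norethindrone". Neither gives a scale, an exposure measure or a margin.

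The Design section gives one strength of each product: "Subjects in each group will be assigned either 0.35mg norethindrone or 5 mg norethindrone acetate as their initial therapy". After the washout, "They will do the above with the opposite therapy", so each subject takes both regimens. Nobody takes a second strength of either product, and the two products share no common dose.

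The Statistical Analysis Plan has two steps: "Serum Levels of norethindrone were averaged across all subjects on days 1 through 7", and "Serum levels of norethindrone were then averaged across all subjects on hours 0-8 on day 8 of the study". Both are done separately by drug, with standard deviations. The plan contains no area under the curve, ratio, dose normalisation or statement about dose proportionality, and the documents do not mention that the two tablets differ in norethindrone content.

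**The concern.** Relative bioavailability is exposure per unit of drug given. The planned summaries are raw concentrations under two regimens that deliver very different amounts of norethindrone. Set side by side, they show how much norethindrone circulates under each regimen, which is a legitimate question but a different one from Aim 1 as worded.

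The risk lies in the conclusion. If raw levels differ widely, a reader of Aim 1 may conclude that bioavailability is not comparable, when the difference in content alone would produce that result. If raw levels turned out similar, a reader may conclude that bioavailability is comparable, when similar levels would mean that the acetate delivers far less norethindrone per unit given. Either way, following the plan does not support the stated conclusion. This is the first aim and the only hypothesis.

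**Working it through.** The documents state no dose ratio, margin or sample size, so there is no figure to reproduce.

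**Inputs**
- Strengths: 0.35 mg norethindrone and 5 mg norethindrone acetate (Study Objectives, Design).
- Molecular mass of norethindrone: about 298. The assay section measures it "with the transitions of 299 > 231 for norethindrone" in positive mode; reading 299 as the protonated molecule gives 299 − 1 = 298.
- Molecular mass of the acetate: about 340, that is 298 + 42 for the acetyl group. This is an assumption from chemical structure and is not printed in the documents.

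**Step 1: content ratio**
- Norethindrone in 5 mg of the acetate: 5 × 298/340 = 4.38 mg.
- Content ratio R = 4.38/0.35 = 12.5 (12.52 before rounding).
- By label milligrams, with no mass assumption: 5/0.35 = 14.3.

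**Step 2: what the raw contrast would show**

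Let exposure = F × D^b, where D is norethindrone content, F is bioavailability and b = 1 means dose proportionality. The raw ratio of acetate to norethindrone is F_rel × R^b. With equal bioavailability (F_rel = 1):

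| b | Raw ratio 12.52^b |
|---|---|
| 0.9 | 9.7 |
| 1.0 | 12.5 |
| 1.1 | 16.1 |

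Conversely, suppose raw exposures counted as comparable when their ratio fell within 0.80 to 1.25 (illustrative limits; the documents give none). With b = 1, F_rel would have to lie between 0.80/12.52 = 0.064 and 1.25/12.52 = 0.100.

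**Step 3: what a normalised ratio would need**

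Dividing each exposure by its norethindrone content gives an apparent ratio of F_rel × R^(b−1). It equals F_rel only if b = 1. Otherwise it is multiplied by:

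| b | Factor 12.52^(b−1) |
|---|---|
| 0.90 | 0.78 |
| 0.95 | 0.88 |
| 1.00 | 1.00 |
| 1.05 | 1.13 |
| 1.10 | 1.29 |

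The factor stays within the illustrative 0.80 to 1.25 when |b − 1| ≤ ln(1.25)/ln(12.52) = 0.088.

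**Step 4: can the trial check b?**

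No. With one strength per product, product and dose always change together. The crossover removes stable differences between people, but within each person the switch of product is also the switch of dose. Adding an area under the curve or a confidence interval leaves the same single contrast.

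**The case against.** The strongest reply is that the aims and the hypothesis always name both products with their strengths. Aim 1 can therefore be read as a comparison of regimens, and the point becomes one of terminology in a descriptive, non-randomised pilot. No section says that a difference will be attributed to the ester apart from dose. Much of this stands: the regimen comparison is estimable, needs no proportionality assumption and requires no redesign. What does not stand is leaving the word bioavailability in place, because it asks for a per-unit comparison that the planned analysis does not make.

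A reader might infer three stronger things that the documents do not support.

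- *That relative bioavailability cannot be identified on any scale.* A content-normalised ratio is identified once dose proportionality is assumed. That assumption cannot be tested here, but it can be stated and varied.
- *That the plan divides by the wrong milligrams.* It divides by nothing. Label milligrams would matter only if a normalised ratio were added: they would lower it by the factor 12.52/14.29 = 0.876, about 12%.
- *That mild non-linearity could create or reverse the finding.* On the raw scale, the only one planned, it could not: with equal bioavailability the ratio is 9.7 to 16.1 for b from 0.9 to 1.1, and reaching 1.25 would need b of about 0.09. The sensitivity concerns only a normalised ratio.

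It is also fair to say that nothing in the documents suggests b differs from 1. The exponents and the 0.80 to 1.25 limits are illustrations.

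**Conclusion.** The point holds in this form: the analysis as written estimates the relative norethindrone exposure of the two regimens as taken, and cannot by itself support a statement about bioavailability. The gap is a content ratio of about 12.5, which rests on an acetate mass of about 340; without that assumption it is 14.3 and the conclusion is the same. A bioavailability reading needs two things that the plan lacks: normalisation by norethindrone content, and a stated assumption of dose proportionality across that range, which this design cannot test. Under the power model, an exponent of 0.9 or 1.1 would multiply a normalised ratio by 0.78 or 1.29. This is more than a missing detail, because it determines what the trial may conclude on its first aim. It is not a reason to call the data uninformative.

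**What to change.** - Reword Aim 1, the hypothesis and the conclusion to *relative norethindrone exposure of 5 mg norethindrone acetate versus 0.35 mg norethindrone as taken*.
- If a bioavailability ratio is also reported, make it secondary. Compute it within subject, normalise by norethindrone content (4.38 mg and 0.35 mg, with the mass conversion shown), and give a confidence interval.
- State the proportionality assumption beside that ratio. Show the factor for b = 0.9, 1.0 and 1.1 (0.78, 1.00, 1.29), labelled as illustrative.
- Say which exposure measure is used. The only serial sampling is this: "On day 8 subjects stopped taking their medication, and initiated pharmacokinetic (PK) testing with hourly blood draws for 8 hours to assess their norethindrone levels". An area over those 8 hours covers only that window, and the report should say so.
- Do not attribute a difference to the ester independently of dose.

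The cost is wording, one secondary ratio and a three-row table. It needs no further subjects or samples, and no dose change is proposed. The downside is a slightly narrower claim. Because the Methods and analysis are written in the past tense, the change can be made at the reporting stage, labelled as a clarification of what is estimated.

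### Aim 1 and the hypothesis concern relative bioavailability, but the SAP plans only per-treatment means and SDs: no within-subject ratio, no confidence interval, and no stated scale for comparability

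*Combined protocol and SAP*

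**What the plan says.** Under Study Objectives, Specific Aim 1 is "To assess the relative bioavailability of norethindrone in individuals taking 5mg norethindrone acetate vs 0.35mg norethindrone", and the single hypothesis is "Hypothesis: The relative bioavailability of norethindrone will be comparable in individuals taking 5mg norethindrone acetate vs 0.35mg norethindrone". No range, margin or scale is attached to it.

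The Design and Study Design sections describe two phases per subject. After the first drug there is a one-month washout, "after which the above was repeated with the opposite medication". The order followed recruitment: the first half of recruits began with norethindrone (NET) and the second half with norethindrone acetate (NETA), without randomisation. Study Design nevertheless labels the trial differently: "This is a cross-sectional pilot study examining serial plasma concentrations of norethindrone".

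The Statistical Analysis Plan is one short paragraph. "Serum Levels of norethindrone were averaged across all subjects on days 1 through 7", for each drug. "Serum levels of norethindrone were then averaged across all subjects on hours 0-8 on day 8 of the study", again for each drug. In both cases, "Standard deviations for each of these averages were calculated". Nothing else is planned.

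**The concern.** Aim 1 names a comparison, and the SAP does not make one. Followed exactly, it produces two columns of averages, one per drug, which the reader must compare by eye. It gives no AUC or other exposure summary, no NETA/NET ratio and no statement of how uncertain a ratio would be.

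The design's main strength is also left unused. Each woman is her own control, so differences between women can be removed from the comparison. Averaging over subjects within each treatment discards that link.

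Finally, the hypothesis cannot be judged until the plan says what is being compared: exposure from the two tablets as given, or exposure per mg. At doses this far apart, one result can support the hypothesis on one reading and contradict it on the other.

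**Working it through.** The plan states no sample size, variability, margin or CI level, so there is no figure of its own to reproduce.

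**1. What the planned summaries can yield.** If the day 8 averages are taken hour by hour, the trapezoidal AUC of the mean profile (weights 0.5, seven 1s, 0.5) equals the mean of the subjects' AUCs, provided the same subjects contribute at every hour. A crude ratio of mean exposures could then be worked out afterwards.

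**2. What they cannot yield.** For a within-subject difference D between treatments A and B,

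Var(D) = s_A² + s_B² − 2ρ·s_A·s_B.

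The SAP reports the SDs but not the within-subject correlation ρ. With equal SDs s, SD(D) = s·√(2(1 − ρ)):
- ρ = 0: 1.41s
- ρ = 0.5: 1.00s
- ρ = 0.9: 0.45s

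The paired uncertainty is therefore not fixed by the planned output. The subject-level concentrations do fix it.

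**3. The scale of comparability.** The doses, from Study Objectives, are 5 mg NETA and 0.35 mg NET.
- Dose ratio by mass: 5/0.35 = 14.3.
- Equal exposure at the doses given means a per-mg ratio of 0.35/5 = 0.070.
- Equal exposure per mg means a ratio at the doses given of 14.3, under dose-proportional kinetics.

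**4. Precision of an added ratio (n and CV are assumptions).** The 95% CI is the ratio multiplied and divided by exp(t × √(2·s_w²/n)), where s_w² = ln(1 + CV²) and CV is the within-subject coefficient of variation. Simple paired differences have n − 1 degrees of freedom; a model with a period term has n − 2.

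| n | CV | factor, n − 1 df | factor, n − 2 df |
|---|---|---|---|
| 12 | 20% | 1.19 | 1.20 |
| 6 | 30% | 1.55 | 1.60 |
| 4 | 50% | 2.90 | 4.21 |

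For n = 6, for example, √(2 × 0.0862/6) = 0.1695; with t = 2.776 on 4 df, exp(0.4706) = 1.60.

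**5. Why period matters.** Let π be the period effect on the log scale, with n1 completers on NET first and n2 on NETA first. The simple mean of the paired log differences estimates the treatment effect plus π(n1 − n2)/(n1 + n2). With 8 and 4 completers, one third of π enters the estimate; with equal numbers, none does. Order was not randomised and completer numbers are not given, so a period term is needed.

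**6. Timing of the day 8 curve.** Study Design says "On day 8 subjects stopped taking their medication, and initiated pharmacokinetic (PK) testing with hourly blood draws for 8 hours". This can mean that the last dose was on day 7, so that hours 0 to 8 fall roughly 24 to 32 hours after dosing, or that the curve follows a dose. The half-lives in Background (8 and 51.5 hours) illustrate what depends on this. After 24 hours of simple decay, 2^(−24/8) = 12.5% and 2^(−24/51.5) = 72% would remain. The documents do not establish that 51.5 hours governs measured norethindrone, so this is only an illustration. On the late reading, the AUC ratio could reflect persistence rather than bioavailability.

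**The case against.** The strongest reply is that this is a self-described pilot with a feasibility survey, and descriptive reporting is legitimate. That stands as far as tests and powered margins go: none is needed. It does not excuse leaving out the descriptive quantity that Aim 1 names.

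A second reply is that the intended scale is clear enough. The title, the aims and the hypothesis all name the doses, Aim 2 concerns concentrations, and the SAP averages unnormalised levels. This largely stands. A reader might infer that the two readings are equally supported, but the documents lean towards exposure at the doses given. The per-mg reading rests only on the term relative bioavailability. What remains is that the plan never says so.

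A third reply is that Methods and the SAP are in the past tense, so a ratio added now would be post hoc. That also stands. It limits how the ratio may be presented, not whether it should be reported.

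A reader might also infer that the trial cannot answer Aim 1 at all. The documents do not support this. Concentrations are measured for each subject in both phases, and only the planned summary lacks the ratio. Nor does the 14.3-fold dose gap show that the hypothesis is false; it shows how far apart the two readings lie.

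**Conclusion.** The concern holds as an omission in the planned analysis. Followed exactly, the SAP does not report the exposure ratio on which Aim 1 and the only hypothesis rest, gives it no CI and makes no use of the within-subject design. At best, a crude ratio of mean profiles could be derived from its output. The undefined scale is a separate gap, worth 14.3-fold by mass if kinetics are dose-proportional.

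The precision figures rest on assumed sample sizes and CVs. On those assumptions, the period-adjusted 95% CI runs from the ratio times or divided by 1.20 to the ratio times or divided by 4.21, so the estimate could be useful or very imprecise. Whether the day 8 AUC can stand for bioavailability at all depends on a dosing time that the documents leave unclear. This should be fixed, and it is cheap to fix.

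**What to change.** 1. Reconcile the Design and Study Design sections on when the last dose was taken relative to the day 8 draws.
2. For each subject and phase, compute the trapezoidal norethindrone AUC over day 8 hours 0 to 8. According to that timing, label it either partial exposure after a dose or a late post-dose (persistence) segment. If it is the latter, do not present it as relative bioavailability.
3. Report the within-subject NETA/NET geometric mean ratio with a CI, its level stated, from log AUC with period (and sequence) terms. Give the number of subjects with both phases.
4. Give the ratio at the doses given as the main estimate, and the same ratio and limits divided by the dose ratio as a secondary one. State the dose basis and the linearity assumption, and say which estimate the hypothesis refers to.
5. Label the ratio post hoc if it was not specified before the data were seen. Give no conclusion of comparability unless a range was set in advance.
6. Describe the study as a two-period, non-randomised crossover in place of the cross-sectional label.

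The cost is a few SAP sentences and a short analysis of samples already described, with no new visits or draws. The drawbacks are a CI that may be wide, a window of only eight hours, and a secondary estimate that relies on linear kinetics across a 14.3-fold dose range.

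### Every subject takes both drugs, but the SAP plans no within-subject NETA–NET contrast or interval; unrandomised order, confounded with early versus late enrolment, is a secondary limitation

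*Combined protocol and SAP*

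**What the plan says.** The Study Design section states "There was no randomization process". It then sets the order of treatment by recruitment: "The first half of subjects recruited were assigned to NET as their initial intervention" and "The second half of subjects were assigned to NETA as their initial intervention". Each subject is crossed over: "They then underwent a 1-month washout, after which the above was repeated with the opposite medication".

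The Statistical Analysis Plan has two parts, each done separately for the two drugs. For the daily samples, "Serum Levels of norethindrone were averaged across all subjects on days 1 through 7". For the intensive sampling day, "Serum levels of norethindrone were then averaged across all subjects on hours 0-8 on day 8 of the study". A standard deviation accompanies each average. The section contains nothing else: no difference or ratio between drugs, no test, no interval, no period or sequence term, and no rule for missing samples.

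The Study Objectives are comparative. Aim 1 concerns relative bioavailability, Aim 2 the maximum and minimum concentrations, and the hypothesis is that "The relative bioavailability of norethindrone will be comparable in individuals taking 5mg norethindrone acetate vs 0.35mg norethindrone". No margin is given for comparability.

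**The concern.** The design collects each subject's levels on both drugs, and the analysis does not use that pairing. A reader can divide one average by the other, but the standard deviations describe spread between subjects within a drug. They cannot show how precisely the ratio is known, because that depends on the within-subject correlation, which is not reported. A hypothesis of comparability cannot be judged without that precision.

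The order of treatment adds a second, smaller issue. All NET-first subjects were recruited before all NETA-first subjects. Any difference in level between early and late enrolees, or any shift between phase 1 and phase 2, can then enter a comparison of raw averages unless the analysis removes it. Because averages are taken per day and per hour, a single missed draw would also unbalance the average at that time point.

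**Working it through.** The documents state no sample size, loss, correlation, period effect or margin, so there is no planned figure to reproduce. The values of rho, r, L and the subject numbers below are assumptions.

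**1. Precision.** With n subjects on both drugs, common variance s² and within-subject correlation rho:
- Unpaired SE of the difference = sqrt(2s²/n).
- Paired SE = sqrt(2s²(1 − rho)/n).
- Ratio = sqrt(1 − rho): 0.84 at rho = 0.3, 0.71 at 0.5, 0.55 at 0.7, 0.32 at 0.9.

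The per-drug SDs give s but not rho, so the paired SE cannot be recovered from the planned output.

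**2. Equal halves, complete data.** Let T be the true NETA/NET ratio, r the phase-2/phase-1 level ratio, and L the late/early level ratio.
- Early half: NET = 1 (phase 1), NETA = T·r (phase 2).
- Late half: NETA = T·L (phase 1), NET = L·r (phase 2).
- Ratio of raw averages = T × (r + L)/(1 + L·r).
- L = 1: multiplier (r + 1)/(1 + r) = 1, so no bias.
- r = L = 1.2: 2.4/2.44 = 0.98.
- r = L = 1.5: 3.0/3.25 = 0.92.

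A constant proportional period effect therefore cancels from the ratio of averages only if early and late enrolees have the same level.

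**3. Log within-subject differences.**
- Early half: log T + log r. Late half: log T − log r. L has dropped out of both.
- The mean of the two sequence means is log T, so r drops out as well.

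**4. Unequal sequences or loss, raw averages.**
- Subjects with both phases, n1 NET-first and n2 NETA-first: share of an additive period effect entering = (n1 − n2)/(n1 + n2), which is 0 at 5 v 5 and 2/8 = 0.25 at 5 v 3.
- Proportional form at 5 v 3 with L = 1: (5r + 3)/(5 + 3r) = 9.0/8.6 = 1.05 at r = 1.2, and 10.5/9.5 = 1.11 at r = 1.5.
- 6 + 6 enrolled, 2 lost from each before phase 2, phase-1 data kept: the late fraction is 6/10 of the NETA average and 4/10 of the NET average, so 0.20 of an early–late difference enters. With r = 1 the multiplier is 1.12/1.08 = 1.04 at L = 1.2.

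**5. What no period term removes.** If r differs between halves, the contrast in step 3 is multiplied by sqrt(r_early/r_late): sqrt(1.2/1.0) = 1.095, and sqrt(1.5/1.0) = 1.22 as an outer case.

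**6. Scale.** The nominal dose contrast is 5/0.35 = 14.3.

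**7. Carry-over of drug.** The Background gives norethindrone acetate an initial rapid disappearance "with subsequent elimination half-life of 51.5 hours". Taking one month as 720 h, 720/51.5 = 14.0 half-lives, which leaves about 0.006%.

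**The case against.** The strongest reply is that no bias is shown. The document reports halves and no losses. The Study Design text has each participant completing an end-of-study survey and diaries returned at the phase-2 Day 8 visit, which leans against dropout without proving full completion. Procedures are the same in both phases, laboratory staff were blinded, and the assay uses an isotope-labelled internal standard, so a large period effect from measurement is unlikely. No mechanism is described that would make the period effect differ between early and late enrolees. The study calls itself a pilot, and the lack of randomisation is openly disclosed.

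Most of this stands, and it limits the allocation part to a secondary point. It does not answer the main one. The missing paired contrast and interval would remain under perfect randomisation, and pilot status does not supply the comparison that the stated aim and hypothesis need. Nor do laboratory blinding and the internal standard address changes in the subjects themselves. Dosing was self-administered and unblinded, with a dosing window and up to an hour before sampling.

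A reader might infer three stronger things that the documents do not support:
- *The NETA–NET comparison is biased by the allocation.* That needs unequal numbers, losses, or period and cohort effects that nobody has reported.
- *Sequence and calendar time are the same variable.* Sequence is a two-level split of recruitment order. Enrolment dates vary within each half, so a smooth date trend is not wholly aliased with it.
- *Drug from phase 1 contaminates phase 2.* On the stated half-life, what remains is negligible.

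**Conclusion.** The concern holds for the analysis. Aim 1 and the comparability hypothesis have no planned estimate with a valid precision, although the paired data exist. The precision forgone depends on an unreported correlation: the paired SE would be 0.71 of the unpaired SE at rho = 0.5 and 0.55 at 0.7. This should be corrected.

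The order of treatment is a limitation of unknown size. With equal, complete halves the illustrative multipliers on the ratio of raw averages are 0.98 and 0.92. With unequal sequences or loss, the examples worked here give 1.04 to 1.11. All rest on assumed inputs. None would overturn a statement that unadjusted exposure differs several-fold. They would matter more for a claim of comparability, for which no margin is stated.

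**What to change.** The study is reported in the past tense, so the main change is a re-analysis.

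1. For each subject with both phases, compute log NETA minus log NET for stated exposure measures: AUC over day-8 hours 0–8, the mean of the day 1–7 levels, and the maximum and minimum observed levels (Aim 2). State a rule for values below quantification before taking logs. The lowest standard of 1 ng/mL divided by 5 implies about 0.2 ng/mL in plasma. Average the two within-sequence means and back-transform to a ratio with a confidence interval. Keep the per-drug averages as description.
2. Report numbers enrolled and completing, and results by sequence and period.
3. State as a limitation that a period effect differing between early and late enrolees cannot be separated from the drug effect.

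Randomising sequence is advice for a follow-on study only; it cannot repair this one.

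Cost: no new subjects, visits or samples. Subjects with one phase do not contribute to the contrast. Its variance relative to the unadjusted mean paired difference is (n1 + n2)²/(4·n1·n2): 1.00 at equal numbers and 64/60 = 1.07 at 5 v 3. The exposure measures and the quantification rule are now chosen after data collection, and the report should say so.
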